3.1.2. Tapering period

For subjects receiving oral corticosteroids during the study treatment period, a tapering of steroids should start at week 4 at a rate of prednisone or prednisone equivalent 5 mg/week for 4 weeks. However, this study procedure is left to the Investigator's discretion.

3.1.3. Dose limiting toxicity (DLT)

A dose limiting toxicity (DLT) is defined as a grade 3 or higher adverse event as defined by the Common Terminology Criteria for Adverse Events (CTC-AE v4.0) considered by a safety review board as probably or definitely related to study treatment. The first three subjects will be enrolled first and followed up for at least 2 weeks of treatment. If more than one DLT occur of the first three treated subjects, then the enrolment of additional subjects will be stopped, otherwise the enrolment of planned subjects will be confirmed.

In addition, in case of a life threatening (grade 4) adverse reaction enrolment and treatment of ongoing subjects will be immediately discontinued.

In both cases, enrolment will only be resumed upon the decision of the sponsor if the Data Safety Monitoring Board can conclude that the causality of the event was unrelated or unlikely related to study treatment.

3.1.4. Data Safety Monitoring Board

An independent Data Safety Monitoring Board (DSMB), with expertise and experience in the pathology, and without direct involvement in the conduct of the trial, will be set up specifically to guarantee effective protection of subjects, insure the ethical conduct of the trial, benefit/risk ratio of the trial, and to ensure the independent review of the scientific results during the trial and at the end of the trial.

The DSMB will meet first after the 3 first subjects are enrolled and treated for at least 2 weeks and then every group of 3 subjects. Besides, the DSMB may recommend the early termination of the trial at any time if an unacceptable toxicity occurs.

The DSMB has only a consultative role; it will inform the sponsor who will decide whether the DSMB recommendation will be followed. A DSMB charter must be available upon submission of the trial (initial protocol) to the respective competent authorities.

3.2. Duration of study participation

Eligible subjects will be enrolled in the present study at the screening visit 2 weeks prior to the first dosing. Subjects will be treated for 8 weeks. All subjects willing to carry on the study treatment will be able to take part in an open-label study (ABX464-102).

In any other cases, the subjects will exit the study (EoS visit to be performed within a week after last dosing) and will be treated according to the standard of care.

Thus, the total duration of the study participation is 11 weeks.

4. STUDY POPULATION

4.1. Number of Subjects/Centers

30 subjects will be randomized in this study. These subjects will be enrolled in up to 20 sites located in France, Belgium, Spain, Poland, Germany, Czech Republic, Austria and Hungary.

4.2. Eligibility Criteria

4.2.1. Inclusion Criteria

A subject will be eligible for inclusion in this study only if ALL of the following criteria apply:

- Men or women age 18 75 years;
- Diagnosis of moderate to severe active UC confirmed by endoscopy and histology at least 12 weeks prior
 to screening visit. Moderate to severe active UC defined by Mayo Clinic Score (MCS) of 6 to 12 inclusive (on
 a scale of 0-12). Moderate to severe active UC should be confirmed at screening visit with a centrally read
 MCS endoscopy score of at least 2 (on a scale of 0-3);
- Subjects receiving oral corticosteroids must have been on a stable dose of prednisone or prednisone equivalent ≤20 mg/day) or on beclomethasone diproprionate (≤5mg/day) or on budesonide MMX (≤9mg/day), for ≥2 weeks before the screening visit;
- Topical corticosteroids and topical 5-aminosalicylic acid preparations must have been withdrawn ≥2 weeks before the screening visit due to inefficacy or intolerance;
- Subjects who are on oral 5-aminosalicylic acid must have been on a stable dose ≥4 weeks before the screening visit;
- Subjects who are receiving immunosuppressants in the form of azathioprine, 6-mercaptopurine, or methotrexate needed to be on a stable dose for 4 weeks before the screening visit. Subjects taking methotrexate also are advised to take folic acid 1 mg/day (or equivalent) supplementation if there is no contraindication;
- Subjects on probiotics (e.g., Culturelle® [Lactobacillus GG, i-Health, Inc.], Saccharomyces boulardii) must be
 on stable doses for 2 weeks before the screening visit;
- Subjects on antidiarrheals (e.g., loperamide, diphenoxylate with atropine) must be on stable doses for 2 weeks before the screening visit;
- Subjects who have previously received anti-tumor necrosis factor (TNF) therapy or vedolizumab must have discontinued therapy ≥8 weeks before the screening visit due to inefficacy or intolerance;
- Subjects previously treated with cyclosporine or tacrolimus must have discontinued therapy ≥4 weeks before the screening visit due to inefficacy or intolerance;
- Subjects previously treated with tube feeding, defined formula diets, or parenteral alimentation/nutrition must have discontinued treatment 3 weeks before the screening visit;
- Subjects with hematological and biochemical laboratory parameters as follows and within 14 days of baseline:
 - Hemoglobin > 9.0 g dL-1;
 - Absolute neutrophil count ≥ 750 mm⁻³;
 - Platelets ≥ 100,000 mm⁻³;
 - o Total serum creatinine ≤ 1.3 x ULN (upper limit of normal);
 - o Creatinine clearance > 50 mL min-1 by the Cockcroft-Gault equation within 60 days of entry;

- Total serum bilirubin < 1.5 x ULN;
- o Alkaline phosphatase, AST (SGOT) and ALT (SGPT) < 1.5 x ULN;
- Subjects should be able and willing to comply with study visits and procedures as per protocol;
- Subjects should understand, sign and date the written voluntary informed consent form at the screening visit prior to any protocol-specific procedures being performed;
- Subjects should be affiliated to a social security regimen;
- Females and males receiving the study treatment and their partners must agree to use a highly effective contraceptive method during the study and for 3 months after end of study or early termination. Contraception should be in place at least 2 weeks prior to study participation. Women must be surgically sterile or if of childbearing potential must use a highly effective contraceptive method. Women of childbearing potential (WOCBP) will enter the study after confirmed menstrual period and a negative pregnancy test. Highly effective methods of contraception include: true abstinence, intrauterine device (IUD) or hormonal contraception associated with inhibition of ovulation, intrauterine hormone releasing system, bilateral tubal occlusion, vasectomized partner. True abstinence is defined when this is in line with the preferred and usual lifestyle of the subject. In each case of delayed menstrual period (over one month between menstruations) confirmation of absence of pregnancy is required. This recommendation also applies to WOCBP with infrequent or irregular menstrual cycle.

4.2.2. Exclusion Criteria

The following criteria should be checked at the time of screening. If ANY exclusion criterion applies, the subject will not be included in the study:

- Subject with Crohn's Disease (CD), indeterminate colitis (IC) or presence or history of fistula with CD;
- History of toxic megacolon, abdominal abscess, symptomatic colonic stricture or stoma; history or is at imminent risk of colectomy;
- History or current evidence of colonic dysplasia or adenomatous colonic polyps. Subject with severe gastrointestinal complications; e.g., short bowel syndromes, obstructing strictures, recent or planned bowel surgery, lleostomy and/or colostomy, recent bowel perforation;
- Subject with significant and known active infections at screening such as infected abscess, positive for Clostridium difficile (stool antigen and toxin), CMV, TB and recent infectious hospitalization;
- Acute, chronic or history of clinically relevant pulmonary, cardiovascular, hepatic, pancreatic or renal
 functional abnormality, encephalopathy, neuropathy or unstable CNS pathology, angina or cardiac
 arrhythmias, or any other clinically significant medical problems as determined by physical examination
 and/or laboratory screening tests and/or medical history;
- Acute, chronic or history of immunodeficiency or autoimmune disease;
- History of malignancy unless there has been surgical excision that is considered to have achieved cure;
- Active malignancy that may require chemotherapy or radiation therapy;
- Seizure disorder or any history of prior seizure;
- Serious illness requiring systemic treatment and/or hospitalization within 3 weeks prior to baseline;
- Pregnant or breast-feeding woman;
- Active drug or alcohol abuse or dependence;
- Use of any investigational or non-registered product within 3 months preceding baseline;
- Any condition, which in the opinion of the investigator, could compromise the subject's safety or adherence to the study protocol.

5. STUDY ASSESSMENTS AND PROCEDURES

5.1. Study Flow Chart

A detailed study flow chart (with all assessments) is displayed hereafter.

			Study Treatment Period								
	D-14	Randomization	D0	D7	D14	D21	D28	D42	D56	D63- EOS	
Time Window	±3 days			±2 days	±2 days	±2 days	±2 days	±4 days	±4 days	±2 days	
Obtained Inform Consent	X										
Check of IN/EX Criteria	Х	X									
Physical Examination	X		Х	X	X	X	X	X	Χ	X	
Body Weight (kg)	Х		X	X	X	X	Х	Х	X	X	
Height Measurement (cm)	X										
Medical History and Concomitant Medications	Х			-							
Vital signs	X		X	X	X	X	X	X	X	X	
ECG (12 lead)	X		X				X		X	Х	
Randomization		X		1							
Blood Pregnancy test (wocse)	X		X	1			X		X		
Hematology + Blochemistry	Х		X	X	Х		Χ		X	Х	
Mayo score (Total or Partial)	X		X	X	X	Х	X	X	X.	X	
Faecal calprotectin			X				X		Х	X	
Rectal microbiota	X						 	1	X		
Sigmoldoscopy	X		 					1	Х		
SF-38 (Questionnaire)			Х			ļ	X]	X		
ABX464/placebo treatment dispensation and subject diary review			×				X				
Blood samples drug pK			X,				Χ·				
Samples for miRNA (Paxgene tubes)			Х				х		X		
Adverse Events recording		I	X	X	l X	X	Х	X	X	 	

^{*} Applicable to the first 9 subjects randomized / PK predose, 0.5, 1, 1.5, 2, 2.5, 3, 4, 8 and 12 post-dose

5.2. Study conduct

It is the investigator's responsibility to ensure that all the assessments are carried out during each visit and that the intervals between visits/follow-ups are adhered to.

5.2.1. Screening Visit (14 \pm 3 days prior to Day 0)

The subject will be informed about the general aspects of the study and will sign the screening informed consent form. The subject number will be allocated once the subject will be created in the eCRF. Only when consent has been given may further study procedures be carried out. During the screening phase, the following assessments will be performed:

- Signed informed consent form;
- · Demographic data: date of birth and gender;
- · Body weight and height;
- Medical history;
- Physical examination and vital signs;
- Hematology and Biochemistry including pregnancy test for all women of childbearing potential;
- 12 leads ECG;
- · Sigmoidoscopy with rectal/sigmoidal biospies;
- Rectal Microbiota sampling (Swab);
- Total Mayo Score;
- Clostridium difficile (stool antigen and toxin), CMV, TB;
- Give the "Subject Diary" and instruct the subject how to use it.

- Record all medications received within 3 months prior to baseline and note if the medication is continuing;
- Inclusion/exclusion criteria will be verified globally.

5.2.2. Randomization procedure

The randomization procedure does not require a site visit of the subject. The Investigator needs to check the inclusion/exclusion criteria with respect to the procedures performed at D-14 visit and if applicable proceed with the subject randomization throughout the eCRF.

5.2.3. Baseline (First dosing day / D0)

- SF-36 questionnaire (as the first visit procedure);
- Physical examination and vital signs;
- Body weight;
- 12 leads ECG;
- Pharmacokinetics blood samples (Applicable to the first 9 subjects randomized);
- Hematology & Biochemistry including blood pregnancy test for all women of childbearing potential;
- Blood sample for miR-124 dosage (PAXgene® tube);
- Faecal calprotectin;
- Partial Mayo Score;
- Adverse Events reporting;
- Dispense study treatment to subject and instruct how to take them (First dosing at site);
- Schedule next subject visits.

5.2.4. D7, D14, D21 Visits (\pm 2 days); D42(\pm 4 days)

- · Physical examination and vital signs;
- Body weight;
- Hematology and Biochemistry (D7 and D14 only);
- Check treatment compliance;
- Review the Subject Diary;
- Partial Mayo Score;
- Adverse Events reporting;
- Schedule next subject visits.

5.2.5. Day 28 (± 2 days) and D56 (± 4 days) Visits

- SF-36 questionnaire (as the first visit procedure);
- · Physical examination and vital signs;
- Body weight;
- Hematology and Biochemistry including blood pregnancy test for all women of childbearing potential;
- Blood sample for miR-124 dosage (PAXgene® tube);
- Pharmacokinetics blood samples (Only at Day 28 visit and applicable to the first 9 subjects randomized);
- 12 leads ECG;
- Faecal calprotectin;

- Sigmoidoscopy with rectal/sigmoidal biopsies only at D56;
- Rectal Microbiota sampling (Swab) only at D56;
- Partial (D28) and Total Mayo (D56) Score;
- · Check treatment compliance;
- Adverse Events reporting;
- · Study treatment dispensation at Day 28 visit;
- Review the Subject Diary;
- Schedule next subject visits.

5.2.6. End of Study Visits (D63 \pm 2 days)

All subjects willing to carry on the study treatment will be able to take part in an open-label study (ABX464-102).

In any other cases, the subjects will perform an End of Study Visit (EoS) within a week after last dosing. Subjects will be treated according to the standard of care since the last day of study treatment.

Following examinations/procedures should be performed:

- Physical examination and vital signs;
- Body weight;
- Hematology and Biochemistry;
- Partial Mayo Score;
- 12 leads ECG;
- Faecal calprotectin;
- Adverse Events reporting.

NB#1: In case of premature discontinuation occurring during the treatment phase (D0-D55), the above examinations should be performed as an End of Study Visit.

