2.2. Secondary Objectives

The secondary objectives are:

- To evaluate the effect of ABX464 on the expression of IL-22 in serum and rectal/sigmoidal tissue compared to placebo in Subjects with Moderate to Severe Active Ulcerative Colitis.
- To evaluate the effect of ABX464 on miR-124 expression in whole blood (PAXgene®) and in tissue (RNA later) vs placebo in Subjects with Moderate to Severe Active Ulcerative Colitis.
- To evaluate the effect of ABX464 on the rectal/sigmoidal infiltrates (Geboes score) vs placebo in Subjects with Moderate to Severe Active Ulcerative Colitis.
- To evaluate the effect of ABX464 on the rectal microbiome compared to placebo in subjects with Moderate to Severe Active Ulcerative Colitis
- To evaluate the effect of ABX464 on endoscopic remission vs placebo in Subjects with Moderate to Severe Active Ulcerative Colitis.
- To evaluate the effect of ABX464 on clinical remission and response vs placebo in subjects with Moderate to Severe Active Ulcerative Colitis.
- To evaluate the effect of ABX464 on Quality of Life (QoL) measured by the SF-36 questionnaire vs placebo in Subjects with Moderate to Severe Active Ulcerative Colitis.
- To assess the Pharmacokinetics parameters of ABX464 in Subjects with Moderate to Severe Active Ulcerative Colitis.

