5.3.4. SF-36 questionnaire (SF-36)

The SF-36 questionnaire is a self-administered questionnaire containing 36 items which takes about five minutes to complete. It measures health on eight multi-item dimensions, covering functional status, well-being, and overall evaluation of health. SF-36 will be filled in by the subjects at Day 0, Day 28 and Day 56 prior to any study procedures.

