7.2. Premature trial discontinuation

A subject must be withdrawn at any time from the study for the following reasons:

Subject's premature trial discontinuation could occur for the following reasons:

- Investigator's decision;
- An Adverse Event or an intercurrent condition that preclude continuation of treatment;
 - o Specifically, an increase ≥ 2.0 x ULN in liver transaminases (AST/SGOT and/or ALT/SGPT), in Alkaline phosphatase or in total bilirubin should be considered a treatment discontinuation criterion
- Worsening of the UC defined as a 2-point increase from the screening MCS with 3 days of continuous rectal bleeding confirmed by flexible sigmoidoscopy with an endoscopy subscore of 2 points or higher;
- Major protocol violation;
- Subject's decision;
- · Withdrawal of consent;

A subject who prematurely exits the study for a non-drug related reason, will be replaced (i.e. an additional subject will be randomized and receive the next treatment allocation. This may or may not be the same treatment as the withdrawn subject).

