7.3. Study Discontinuation

All subjects, regardless of the completion or premature discontinuation, should perform the End of Study Visit according to the study flow-chart.

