10 STATISTICAL METHODS

10.1 GENERAL PRINCIPLES

All statistical methods will be based on the International Conference on Harmonisation (ICH) E9 document "Statistical Principles for Clinical Trials".

Data will be summarised by treatment group. A total column showing all patients will be included for baseline and safety summaries. Where appropriate, data will also be summarised by visit with summaries for each visit attended as scheduled and an additional summary for final (last scheduled visit or early withdrawal). The format of the summaries is defined in the shells at the end of this document.

In summary and analysis tables of continuous variables, standard descriptive statistics (N, mean, standard deviation [SD], median, minimum and maximum) will be presented. Quartiles, least squares mean (LS mean), standard error (SE) and 95% confidence interval (CI) will be presented in the statistical analysis outputs as appropriate. For PK summaries, arithmetic mean (AM), geometric mean (GM) and coefficient of variation (%CV) will be used to summarise the data. The minimum and maximum statistics will be presented in summary tables to the same number of significant figures as the original data. The mean/AM, median, LS mean, GM, CI, SD and SE will be presented to one more significant than the original data.

For numeric data which includes non-numeric values (e.g. PK data reported as below limit of quantification [BLQ] or lab results reported as < 10 or > 100) the following principles will be applied when summarising the data:

- BLQ will be replaced with a value that is ½ of the lower limit of quantification (LLQ)
- Results reported as < x will be treated in the same way as BLQ with LLQ=x
- Otherwise AM, GM, SD, Cl and %CV will not be calculated
- Whenever meaningful, minimum, median and maximum will be presented based on the reported data (e.g. minimum = <10, median = 20, maximum = >100)

In summary tables of categorical variables, the number of non-missing observations by category will be presented with percentages. The number of missing observations will also be presented when non-zero. Unless otherwise specified, the denominator for each percentage will be the number of non-missing observations within the column. All percentages will be presented to one decimal place.

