10.2 Missing Data

There will be no imputation of missing data in this study.

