11.3.2 Other Secondary Efficacy Endpoints

The change from baseline to Weeks 4 and 8 in faecal calprotectin levels will be descriptively summarised and analysed using a general linear mixed (analysis of covariance (ANCOVA)) model for repeated measures fitted with treatment and stratification factors and visit as fixed effects along with a treatment-by-visit interaction term. The treatment effect (taken from the treatment-by-visit interaction terms at Week 4 and 8), 95% CI and p-values will be presented (*Table 14.2.2.1*).

The change from screening to Week 8 in TMS and the change from baseline to Week 4 and 8 in PMS will be descriptively summarised (*Tables 14.2.2.2* and 14.2.2.3).

The number and proportion of subjects achieving endoscopic remission at Week 8 and the number and proportion of subjects achieving mucosal healing at Week 8 will be descriptively summarised (*Table 14.2.2.4*). Endoscopic remission is defined as a Mayo endoscopic sub-score of zero and mucosal healing is defined as a Mayo endoscopic sub-score of less than or equal to one.

The number and proportion of subjects achieving a clinical response at Week 8 will be descriptively summarised (*Table 14.2.2.5*). Clinical response is defined as the reduction of at least 3 points in TMS and

30% from baseline score with a decrease of at least 1 point in bleeding sub-score or an absolute bleeding sub-score of 0 or 1.

The scores and changes from baseline in the MH and PH component summary measures of the SF-36 questionnaire at Week 4 and Week 8 will be descriptively summarised (*Table 14.2.2.6*).

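### The SF-36 comparison rests on completers, because the SAP tabulates it only on the per-protocol set and early leavers give no exit score; the direction of any bias is unknown

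*Protocol*

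**What the plan says.** Protocol 2.2 lists as a secondary objective: "To evaluate the effect of ABX464 on Quality of Life (QoL) measured by the SF-36 questionnaire vs placebo". Protocol 5.3.4 fixes the schedule: "SF-36 will be filled in by the subjects at Day 0, Day 28 and Day 56 prior to any study procedures". The flow charts (protocol 5.1, SAP 16.1) agree and show no SF-36 at the Day 63 End of Study visit.

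That visit also serves subjects who stop early. After a list that covers physical examination, weight, laboratory tests, Partial Mayo, ECG, calprotectin and adverse events, protocol 5.2.6 adds: "In case of premature discontinuation occurring during the treatment phase (D0-D55), the above examinations should be performed as an End of Study Visit". Protocol 7.3 confirms it: "All subjects, regardless of the completion or premature discontinuation, should perform the End of Study Visit according to the study flow-chart". One listed reason for leaving (protocol 7.2) is: "Worsening of the UC defined as a 2-point increase from the screening MCS with 3 days of continuous rectal bleeding", confirmed by endoscopy.

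On analysis, SAP 11.3.2 says that scores and changes in the two component summaries of the "SF-36 questionnaire at Week 4 and Week 8 will be descriptively summarised". Table 14.2.2.6 is assigned to the per-protocol (PP) set only. SAP 6.3 limits that set to FAS members with no major deviation who completed to Day 56. SAP 11.3 repeats only the primary analysis on the FAS. Protocol 9.2 instead places the efficacy analysis in the FAS. SAP 10.2 states: "There will be no imputation of missing data in this study".

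**The concern.** The comparison is meant to describe the effect of treatment against placebo, but it will describe only subjects who stayed to Day 56 without a major deviation. Exit can be triggered by the disease state that the SF-36 reflects, so those who leave are unlikely to be a random subset. The rule that early terminators count as failures settles a yes/no endpoint such as remission, but it supplies no value for a continuous score.

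Two separate features cause this. The PP restriction discards scores that have been collected. The visit schedule means that exit scores are never collected. The first can be put right at analysis; the second cannot. With about 10 placebo subjects, two leavers are 20% of that arm.

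**Working it through.** **The plan's own figure.** The documents give no figure for the SF-36, for exit rates or for bias. The nearest design figure is the 81% power in protocol 9.4 (0.6 vs 0.2, 20 vs 10 subjects, one-sided 10%). Pooled rate = (20×0.6 + 10×0.2)/30 = 0.467. Null standard error = √(0.467×0.533×(1/10 + 1/20)) = 0.193. Alternative standard error = √(0.2×0.8/10 + 0.6×0.4/20) = 0.167. Power = Φ((0.4 − 1.282×0.193)/0.167) = 81.9%. The figure reproduces and does not depend on the SF-36 schedule.

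**Which scores reach the table.**

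| Exit | SF-36 available after baseline | Table 14.2.2.6 (PP) | On the FAS | FAS plus exit SF-36 |
|---|---|---|---|---|
| Before Day 28 | none | excluded | nothing to add | final row only |
| After Day 28, before Day 56 | Day 28 | excluded, including Week 4 | Week 4 row | Week 4 and final rows |
| Completer without major deviation | Day 28, Day 56 | included | included | included |

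Moving to the FAS alone recovers Day 28 scores but no exit scores. Collecting an exit score alone changes nothing in the table, because PP still removes the leaver.

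**Direction.** Let w be the share leaving early in an arm and g the mean change in completers minus that in leavers. Then

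completer difference − all-subject difference = w_A·g_A − w_P·g_P,

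with A for ABX464 and P for placebo. All inputs below are assumptions, including a true difference of 3 points in favour of ABX464.

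| w_A / w_P | g_A / g_P | Bias | Completer difference |
|---|---|---|---|
| 5% / 20% | 10 / 10 | 0.5 − 2.0 = −1.5 | 1.5 |
| 10% / 30% | 10 / 10 | 1.0 − 3.0 = −2.0 | 1.0 |
| 10% / 10% | 10 / 10 | 0 | 3.0 |
| 10% / 10% | 15 / 10 | 1.5 − 1.0 = +0.5 | 3.5 |
| 20% / 10% | 10 / 10 | 2.0 − 1.0 = +1.0 | 4.0 |

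The benefit shrinks only when w_P·g_P exceeds w_A·g_A. Even with true exit rates of 10% on ABX464 and 20% on placebo, in 20 and 10 subjects the observed placebo share is the higher with probability 0.69, ties with 0.12 and is the lower with 0.20 (rounded).

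**Size in an illustration tied to the 60% and 20% response rates.** Assume changes of +8 in responders, +2 in non-responders who stay and −4 in leavers, and let 25% of non-responders leave (10% of ABX464, 20% of placebo).

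- ABX464, all: 0.6×8 + 0.3×2 + 0.1×(−4) = 5.0; completers: 5.4/0.9 = 6.0.
- Placebo, all: 0.2×8 + 0.6×2 + 0.2×(−4) = 2.0; completers: 2.8/0.8 = 3.5.
- Difference: 3.0 for all, 2.5 for completers, a bias of −0.5 points (−17%).

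The grid lets 10%, 15%, 25% or 40% of non-responders leave, under four change patterns (responder, stayer, leaver): (8, 2, −4), (8, 2, 0), (6, 3, −2) and (10, 2, −5). The bias runs from −1.4% to −37.0%.

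- Largest in percent: (6, 3, −2) at 40%. All: 4.00 − 2.00 = 2.00. Completers: 4.32/0.84 − 2.64/0.68 = 1.26. Bias about −0.74.
- Largest in points: (10, 2, −5) at 40%. All: 5.68 − 1.36 = 4.32. Completers: 6.48/0.84 − 2.96/0.68 = 3.36. Bias about −0.96.

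No cell reaches 1 point. The grid says nothing about direction: it applies one leaving share to 40% and 80% non-responders, so placebo exits are always double and every cell shrinks by construction.

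**The case against.** The protocol is consistent about the SF-36 schedule, so leaving it out of the exit visit is a design choice and not an error. Worsening at exit is already recorded through Partial Mayo and calprotectin, and leavers count as failures for remission. An exit SF-36 is neither a Week 4 nor a Week 8 score. It may be taken up to a week after the last dose, under standard of care, and most items ask about the past four weeks, so for an exit before Day 28 the answer partly covers time before treatment. The illustrated bias is also small beside sampling error: with about 18 and 8 completers and an assumed SD of 6 to 10, the standard error of the difference is about 2.5 to 4.2 points. All of this stands. It limits the weight of the point and means that an exit score can only supplement Week 8. It does not justify leaving collected Day 28 scores out of the Week 4 row, contrary to protocol 9.2.

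A reader might infer more than the documents support:

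- *That the missing exit questionnaire alone causes the completer comparison.* The PP restriction comes first and would remove an exit score too.
- *That any benefit over placebo must shrink.* The 60% and 20% are response rates. Non-response is not exit for worsening, neither document gives exit rates, and protocol 7.2 lists other reasons, such as adverse events and liver-test rises, that could fall more on ABX464.
- *That a planned output cannot be filled.* SAP 10.1 foresees a closing summary that takes in early-withdrawal visits, but only where appropriate and in the format of the shells. The SF-36 shell has no such row, and completers have a Day 56 score.

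**Conclusion.** The point holds as a minor one. The SF-36 summary describes completers because of the PP set and, behind that, because no exit score is collected. This can bias a descriptive comparison in either direction or not at all, depending on exit rates and on how much worse leavers are in each arm; the documents give neither. Under the response-based illustration, which builds in twice as many placebo exits, the bias is below 1 point. With an assumed 10-point gap between completers and leavers and exits of 10% and 30%, it would be 2 points. No test, error rate or sample size is affected, since the SF-36 is summarised without a model or p-value. The case for acting is the low cost, and that without exit scores the bias cannot be assessed either way.

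**What to change.** 1. In SAP 11.3.2 and Table 14.2.2.6, summarise the SF-36 on the FAS, in line with protocol 9.2, and keep PP as supportive. Day 28 scores of later leavers then enter the Week 4 row. Cost: one repeated table and no new data.

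2. In the note to protocol 5.2.6 and in the flow charts, add the SF-36, completed first, to the End of Study visit when that visit replaces the remaining treatment visits. Add a supplementary FAS row to Table 14.2.2.6, labelled *Final (Week 8 or early withdrawal)*, for score and change from baseline, with the number of exit scores and their study days. Cost: a self-completed form of about five minutes (protocol 5.3.4) at a visit that already takes place, for early leavers only, plus a schedule footnote and one table row.

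State beside the row that exit scores come at varying times and that the four-week recall overlaps the pre-treatment period for exits before Day 28. The row supplements the Week 8 summary and does not replace it.
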